3.4.1.4 Additional Analyses of the Primary Efficacy Endpoint(s)

The primary population is the primary efficacy analysis population (TIMI 0-1). Similar analysis will also be performed for the Efficacy Analysis Population with TIMI 0-3, the efficacy analysis population with TIMI 2-3, and the ITT Population.

Non-parametric (distribution-free) methods will be applied to primary endpoint data if applicable.

3.4.1.5 Subgroup Analyses

The primary endpoint of infarct size will be analyzed for the following subgroups. The first set of subgroups are based on baseline characteristics and time of treatment administration.

- Sex: male vs female

- Diabetic vs non-diabetic
- Smoker vs non-smoker
- Infarct location: anterior vs non-anterior
- TIMI Flow Grade 0 vs 1 vs 2 vs 3 pre-pPCI
- TIMI Flow Grade 0 or 1 vs 2 or 3 pre-pPCI
- Above vs below the median door-to-device time
- Above vs below the median symptom onset-to-device time
- Above vs below the median symptom onset-to-door time

The second set of subgroups, outlined in Table 3.2, are based on post-randomization outcomes and will not be used to make comparisons between treatment and placebo.

Table 3.2 Post-randomization Analysis Subgroups

Endpoint	Comparison Groups
Infarct size by culprit vessel location determined by baseline invasive coronary angiography	LAD vs Non-LAD LAD vs Left Circumflex Artery vs Right Coronary Artery
Infarct size by timing of drug administration	Investigational product administration before vs after pPCI Above vs below the median time between Dose 1 and pPCI
Infarct size by post-pPCI TIMI Flow Grade	TIMI Flow Grade 0 vs 1 vs 2 vs 3 post-pPCI TIMI Flow Grade 0 or 1 vs 2 or 3 post-pPCI

Infarct size by lipid and apolipoprotein levels	
Above vs. below the median HDL at baseline
 
Above vs. below the median HDL change from baseline
 
Above vs. below the median apoA1 at baseline
 
Above vs. below the median apoA1 change from baseline

Infarct size by cardiovascular event status	
Any CV event vs no CV event
 
HF Hospitalization vs No HF

LAD = left anterior descending artery; pPCI = primary percutaneous coronary intervention; CV = cardiovascular; HF = heart failure

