4.8 Statistical Evaluation

4.8.1 General Considerations

An initial database lock for the purpose of clinical study analysis and reporting will be performed when the last randomized subject completes the Day 70 to 84 visit or is discontinued prior to that visit; if no subjects are ongoing in the Extended Follow-up period, then this database lock will be considered the final database lock for the study.

If subjects are ongoing in the Extended Follow-up period, a second database lock will occur after all subjects who entered the Extended Follow-up period have completed their Week 25, 39, or 52 visits as needed (see Section 4.2.2) or are discontinued prior to these visits, and this will be considered the final database lock. If the last Extended Follow-up visit occurs before the last Day 70 to 84 visit on the study, the second database lock will not be needed.

The study will be unblinded to the sponsor at the time of initial database lock. The site, subjects, and local CRO personnel will remain blinded to treatment assignment until the final database lock is declared.

Safety data will be generated for the Extended Follow-up period and summarized as an addendum to the clinical study report.

Data will be provided in listings sorted by treatment group, and subject number. Tabular summaries will be presented by treatment group with placebo group combined when appropriate. Categorical data will be summarized by the number and percentage of subjects in each category. Continuous variables will be summarized by descriptive statistics. Baseline values will be defined as the last valid assessment prior to the first administration of investigational product on Day 1. Confidence intervals will be one-sided and nominal p-values will be reported when appropriate. Additional details of statistical analyses will be described in the statistical analysis plan.

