3.4.2.4 Subgroup Analyses

[figure not shown]
The secondary endpoints will be analyzed for the subgroups listed below, which includes a mixture of subgroups defined before and after randomization. As for the primary efficacy endpoint, subgroups defined after randomization will not be used to make comparisons between active and placebo arms.

- Sex: male vs female
- Diabetic vs non-diabetic
- Infarct location: anterior vs non-anterior
- Infarct location: LAD vs non-LAD
- Infarct Location: LAD vs LCX vs. RCA
- TIMI Flow Grade 0 vs 1 vs 2 vs 3 pre-pPCI
- TIMI Flow Grade 0 or 1 vs 2 or 3 pre-pPCI
- TIMI Flow Grade 0 vs 1 vs 2 vs 3 post-pPCI
- TIMI Flow Grade 0 or 1 vs 2 or 3 post-pPCI
- Above vs below the median door-to-device time

- Above vs below the median symptom onset-to-device time
- Above vs below the median symptom onset-to-door time
- Drug administration before vs after pPCI
- Above vs below the median time between dose 1 and pPCI
- Above vs below the median HDL at baseline
- Above vs below the median HDL change from baseline
- Above vs below the median apoA1 at baseline
- Above vs below the median apoA1 change from baseline
- Cardiovascular Event vs No Cardiovascular Event
- HF Hospitalization vs No HF Hospitalization
- Prior statin vs statin naïve
- Baseline LDL-C \leq 100 vs $>$ 100 mg/dL
- Baseline LDL-C \leq 70 vs $>$ 70 mg/dL

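### SAP Table 3.2 bars the arm comparison for baseline HDL, baseline apoA1 and culprit vessel as post-randomisation outcomes, while two device-time splits that end after randomisation escape the bar

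*SAP*

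**What the plan says.** SAP 3.4.1.5 gives two sets of subgroups for infarct size.

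- The first is introduced thus: "The first set of subgroups are based on baseline characteristics and time of treatment administration". It holds nine splits, including pre-pPCI TIMI flow grade (two splits), symptom onset-to-door time, symptom onset-to-device time and "Above vs below the median door-to-device time". No restriction is placed on it.
- The second is Table 3.2, described as "based on post-randomization outcomes and will not be used to make comparisons between treatment and placebo". Among its twelve splits are "Above vs. below the median HDL at baseline", "Above vs. below the median apoA1 at baseline" and, with two splits, "Infarct size by culprit vessel location determined by baseline invasive coronary angiography".

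Protocol 4.8.1 defines a baseline value as the "last valid assessment prior to the first administration of investigational product on Day 1". SAP 3.1 uses the same definition and adds a fallback for missing data that is also pre-dose.

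For the secondary endpoints, SAP 3.4.2.4 gives one list, says that it mixes subgroups defined before and after randomisation, and adds: "As for the primary efficacy endpoint, subgroups defined after randomization will not be used to make comparisons between active and placebo arms". No item is marked as one kind or the other.

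**The concern.** Treatment arms should not be contrasted within groups that treatment may have helped to form. The SAP states that principle and then applies it to variables that treatment cannot have touched.

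The lipid rows matter most. Protocol 1.5 says that the study will determine whether MEDI6012 reduces infarct size by raising HDL-C and apoA1. Whether the effect differs by starting HDL or apoA1 is therefore a natural question, and the SAP as written forbids the comparison that would answer it. If the sponsor reports that comparison anyway, it departs from its own plan. If it follows the plan, the result is missing from a trial that has the data.

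The opposite slip is smaller. The two device-time splits are open to arm comparison although the intervals finish after randomisation, at a stage when site staff and possibly the investigator may know the assignment (Protocol 3.1.1 and 4.6.2).

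**Working it through.** No sample size, power or alpha figure attaches to this point, so there is no plan figure to reproduce. The check sets each split's list against the time at which its value is fixed.

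**Sequence of events.** Subjects are randomised before pPCI (Protocol 3.1.1, SAP 2.2). Blood for PD is drawn before dosing (Protocol 3.1.1). Dose 1 is due before the wire crosses the culprit lesion and is given after PCI only in rare cases (Protocol 4.5.1.4). Angiographic findings may come to light before or after the first dose (Protocol 4.1.7).

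**Table 3.2 (arm comparison barred)**

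| Split | Number | Value fixed | Can assigned treatment change it? |
|---|---|---|---|
| HDL at baseline | 1 | Before Dose 1 | No |
| apoA1 at baseline | 1 | Before Dose 1 | No |
| Culprit vessel | 2 | By the index infarct; read on the initial angiogram | No |
| HDL change, apoA1 change | 2 | After dosing | Yes |
| Post-pPCI flow grade | 2 | After pPCI | Yes |
| Drug before/after pPCI; Dose 1-to-pPCI time | 2 | After randomisation | Possibly |
| CV event; HF hospitalisation | 2 | During follow-up | Yes |

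Total: 1 + 1 + 2 + 2 + 2 + 2 + 2 = 12. Barred although treatment cannot change them: 1 + 1 + 2 = 4 of 12.

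**First list (not barred)**

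| Split | Number | Value fixed | Can assigned treatment change it? |
|---|---|---|---|
| Sex, diabetes, smoking, anterior location | 4 | Before randomisation | No |
| Symptom onset-to-door | 1 | On arrival | No |
| Pre-pPCI flow grade | 2 | On the initial angiogram, before or after Dose 1 | Only if read after Dose 1 |
| Door-to-device, onset-to-device | 2 | At the device, after randomisation | Possible, not shown |

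Total: 4 + 1 + 2 + 2 = 9. Completed after randomisation and outside the bar on timing alone: 2 of 9.

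**Internal consistency.** Culprit vessel and pre-pPCI flow grade come from the same angiogram but sit in opposite lists. If the criterion is when the value is read, they belong together. If it is whether treatment could alter the value, culprit vessel has the stronger claim to be comparable, because flow may change and location does not. Neither criterion gives the SAP's allocation. The first set's heading also promises time of treatment administration, yet both drug-timing splits are in Table 3.2.

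**Secondary endpoints.** The list in SAP 3.4.2.4 has 3 (sex, diabetes, anterior location) + 2 (vessel) + 4 (flow grade) + 3 (onset and device times) + 2 (drug timing) + 4 (HDL and apoA1) + 2 (events) + 3 (statin and LDL-C) = 23 items, none labelled. Read with the baseline definition, baseline HDL and apoA1 are comparable there. Read through the reference back to the primary endpoint, they may inherit the Table 3.2 bar.

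**The case against.** The strongest reply is that little is lost. These are subgroup analyses with no stated alpha or power. Protocol 3.2.2 expects the benefit to lie in larger infarcts, and anterior location and flow grade are both in the unbarred list. The protocol's clinical evidence on HDL links low HDL-C to lower ejection fraction after infarction, which is prognosis and not modification of a drug effect. All of that stands, and it limits the importance of the point. It does not explain why a pre-dose value is called a post-randomisation outcome.

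On culprit vessel, filing by time of reading is arguable, and anterior location, which is the stratification factor, already covers part of the question. The inconsistency with pre-pPCI flow grade remains. On device times, nothing in the documents shows that an IV push over 1-2 minutes, given in both arms, shifts them. The case for marking them rests on their timing alone.

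A reader might infer more than the documents support:

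- **That pre-pPCI flow grade is normally read after Dose 1 and should be barred as well.** No section gives the usual order. Protocol 4.1.7 allows either, and Protocol 4.8.3.4 calls this reading baseline even while comparing it between arms. Barring it would also collide with the primary analysis, which compares arms within flow grade 0-1, and with the planned TIMI 2-3 and 0-3 analyses.
- **That the device times are filed as baseline and will certainly be compared.** The first set's heading also covers time of treatment administration. Comparison within that set is implied by the bar on the other and is not stated.
- **That the same misfiling governs the secondary endpoints.** SAP 3.4.2.4 bars only subgroups defined after randomisation. The fault there is ambiguity.

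**Conclusion.** The point holds. It is clearest for baseline HDL and baseline apoA1, where the SAP's label contradicts the baseline definition in both documents and removes a comparison that the trial could validly report. It holds on consistency for the two culprit-vessel splits, and on timing for the two device-time splits. In all, 4 of 12 splits are barred without cause and 2 of 9 are left open that the SAP's own rule would restrict. The secondary list needs labels.

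This rests on three assumptions: that the baseline lipid values are the pre-dose samples the protocol calls for, that device time is a pPCI time and so follows randomisation, and that arrival precedes randomisation. The primary test, its population and its alpha are not affected. The documents do not establish that baseline HDL or apoA1 modifies the effect of MEDI6012, only that the plan's rationale makes the question worth leaving open.

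**What to change.** In SAP 3.4.1.5:

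1. Move HDL at baseline and apoA1 at baseline from Table 3.2 to the first list, with the MEDI6012-versus-placebo comparison and a treatment-by-subgroup interaction. Keep only the change-from-baseline lipid splits in Table 3.2.
2. Move the two culprit-vessel splits in the same way, for consistency with pre-pPCI flow grade.
3. Mark door-to-device and symptom onset-to-device time as post-randomisation and descriptive only. Symptom onset-to-door remains the pre-randomisation timing subgroup.
4. Leave pre-pPCI flow grade where it is, and say that it defines the primary and supporting populations.
5. Reword the first set's heading so that it matches its contents.

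In SAP 3.4.2.4, label each item as before or after randomisation on the same basis, so that baseline HDL and apoA1 are clearly comparable for the secondary endpoints.

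The cost is an edit to two lists and one table, plus an interaction term in the programming for the moved splits. No new data are needed. The two device-time splits lose their formal arm comparison. The edit should be made before treatment codes are released for the final analysis, so that the choice of comparisons cannot be linked to the results.

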3.4.2 Secondary Efficacy Endpoint(s) and Analyses

3.4.2.1 Secondary Efficacy Endpoint(s)

Secondary efficacy endpoints include ejection fraction (EF) measured by cine MRI at 10–12 weeks post-MI, change in NCPV in the coronary arteries from index CTA to 10–12 weeks post-MI, and myocardial mass and left ventricular volumes at end-systole and end-diastole.

3.4.2.2 Handling of Dropouts and Missing Data

Missing data will not be imputed.

3.4.2.3 Secondary Efficacy Analyses

EF, myocardial mass, and left ventricular volumes will be analyzed using t-test, if appropriate, based on the Primary Efficacy Analysis Population, the Efficacy Analysis Population – TIMI 2-3; Efficacy Analysis Population – TIMI 0-3; as treated, and the ITT Population.

Change from index CTA in NCPV will be analyzed using t-test, if appropriate, based on CTA Analysis, As-treated, and ITT Populations.

Parameters will first be evaluated for normality which will be evaluated using Q-Q plots.

If the distribution appears to be normal, the endpoint will be analyzed by a 2-sample t-test. The treatment effect is estimated by difference in means of MEDI6012 to placebo as well as its 95% CI.

If the distribution appears to be log-normal, the endpoint will be log-transformed due to its skewed distribution and be analyzed by a 2-sample t-test. The treatment effect is estimated by the geometric mean ratio of MEDI6012 to placebo as well as its 95% CI.

Non-parametric (distribution-free) methods will be applied to the endpoint data if applicable.

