Following verbal or written informed consent (per local regulations) and prior to dosing, an assessment will be made of vital signs, and blood samples will be collected for clinical laboratory assessment, PK, PD, and immunogenicity. The [REDACTED] of investigational product should be administered via IV infusion over 1-2 minutes prior to pPCI on Day 1 as soon as possible prior to the first pPCI procedure, defined as the time that the first angioplasty wire crosses the culprit lesion. Following dosing and pPCI, study procedures will be conducted in accordance with the Schedule of Study Procedures. On Day 3 (48±8 hours post [REDACTED] subjects will receive a [REDACTED] dose of investigational product and additional study procedures will be conducted according to the Schedule of Study Procedures.

For Cohort B only, those subjects with creatinine clearance (CrCl) \geq 60 mL/min (Cockcroft Gault equation) within 6 hours will undergo an index coronary computerized tomography angiography (CTA) no earlier than 40 hours following the [REDACTED] dose. It is preferred that the index CTA occur 48-72 hours post Dose [REDACTED], but it may be done up to 5 days post Dose [REDACTED]. Subjects may be discharged following Day 3 assessments, if considered acceptable by the clinical team and investigator.

Following Doses [REDACTED] and [REDACTED] (Cohort A) or Doses [REDACTED] through [REDACTED] (Cohort B), subjects will be monitored for 2 hours in a location with personnel trained in Adult Advanced Life Support with proper resuscitation equipment available.

Outpatient Phase – Cohort A

[figure not shown]
Subjects randomized to Cohort A [REDACTED] regimen) will undergo standard of care treatment post pPCI ([Figure 4](#)) and will follow-up according to the Schedule of Assessments. An end of study cardiovascular magnetic resonance (CMR) will be performed at 10-12 weeks (70-84 days post Dose 1).

Figure 4 Study Flow Diagram for Cohort A: [REDACTED] Regimen

CCU = cardiac care unit; CMR = cardiovascular magnetic resonance (imaging); D = day; ECG = electrocardiogram; ED = emergency department; PCI = percutaneous coronary intervention; STEMI = ST elevation myocardial infarction.

Outpatient Phase – Cohort B

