4.1.4 Additional Study Procedure Requirements

After randomization and prior to study-related imaging procedures, subjects will be required to meet the following criteria for CMR and CTA imaging.

Administration of Gadolinium Contrast for Cardiovascular MRI

MRI is allowed if there is no contraindication to MR imaging (eg, metallic implant, claustrophobia, ICD, pacemaker), but in order for subjects to receive gadolinium contrast, the following requirements must also be met:

- 1 CrCl \geq 30 mL/min (Cockcroft Gault equation) within 7 days prior to the procedure
- 2 No known allergy to gadolinium contrast agents

Coronary CTA

- 1 CrCl \geq 60 mL/min (Cockcroft Gault equation) within no more than 6 hours prior to index CTA and no more than 7 days prior to follow up CTA
- 2 Women must be 40 years of age or older
- 3 No known allergy to iodinated contrast
- 4 No known history of contrast induced nephropathy
- 5 No contraindication to heart rate lowering using betablockers to allow for high quality, low-radiation dose CTA (per-protocol). Please note, if heart rate is well-controlled allowing for a high quality, low radiation CTA without betablocker, then a contraindication to betablocker does not exclude the subject from coronary CTA.
- 6 For follow-up CTA at the end of the study, subjects would need to have undergone index CTA

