¹ Within 20 minutes [REDACTED]^m Fasting for 1-1.5 hours at the 1-1.5 hour timepoint, fasting for ≥6 hours on Days 3-70ⁿ Future use samples will only be obtained if the subject gives consent. Aliquots of future use samples will be stored at the core laboratory and the TIMI biobank.^o In the case of a clinical indication for an intracardiac device (ie, pacemaker, implantable cardioverter-defibrillator), the CMR can be scheduled at an earlier time point, but not prior to 30 days post Dose 1. In addition, if the end of study CMR is determined to be of inadequate image quality by the CMR core laboratory, the subject may return for a repeat CMR within 4 weeks of the end of study window (up to 112 days post Dose 1).^p Index CTA will preferably be performed between 48-72 hours post Dose 1 (may be done up to 5 days post Dose 1) but no earlier than 40 hours post Dose 1. The index CTA scan should not be performed if CABG surgery was carried out prior to the index CTA time point or if one is planned.^q Follow-up coronary CTA imaging will be done only for subjects with index CTA and can occur on a separate visit from CMR imaging, if needed for scheduling purposes. In subjects who have CABG surgery planned, index and follow-up CTA should not be performed. If a subject completes 6 doses of investigational product and is scheduled for CABG surgery, follow-up CTA can be performed earlier to ensure that CTA occurs prior to the CABG surgery, upon approval from the TIMI Hotline or Sponsor. For subjects who have received fewer than 6 doses of investigational product or if CABG surgery has already been performed prior to the CTA time point, the CTA scan should not be performed.

4.2.2 Extended Follow-up Period for Subjects Testing Positive for Anti-Drug Antibodies Plus > 30% Decrease from Baseline in HDL-C at Day 70 to 84 or Presence of a Neutralizing Antibody on Day 70 to 84

Table 10 shows all procedures to be conducted during the Extended Follow-up period for subjects testing positive for ADAs plus > 30% decrease from baseline in HDL-C at Day 70 to 84) or presence of nAb on Day 70 to 84). Assessments should be performed in the order shown in the table. During the Extended Follow-up period, if either the ADA test result becomes negative or the HDL-C is no longer > 30% decreased compared with baseline, the subject does not need to return for any additional Extended Follow-up visit(s) and will be considered as having completed the Extended Follow-up period.

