4.8.3.3 Secondary Efficacy Analyses

Secondary efficacy endpoints include EF measured by cine MRI at 10-12 weeks post-MI, Change in NCPV in the coronary arteries from index CTA to 10-12 weeks post-MI, and Myocardial mass and left ventricular volumes at end-systole and end-diastole.

EF, myocardial mass, and left ventricular volumes will be analyzed similarly to infarct size without the log-transformation of the data.

Change from index CTA in NCPV will be analyzed using t-test based on CTA analysis population.

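### Change in NCPV is compared by an unadjusted t-test although index NCPV is available for every analysed subject; adjusting for it is an optional precision gain, not the correction of an error

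*SAP*

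**What the plan says.** SAP 3.4.2.3: "Change from index CTA in NCPV will be analyzed using t-test, if appropriate, based on CTA Analysis, As-treated, and ITT Populations." If the data look normal, this is a two-sample t-test with a difference in means and a 95% CI. The alternatives are a t-test after log transformation and unnamed non-parametric methods. Protocol 4.8.3.3 agrees: "Change from index CTA in NCPV will be analyzed using t-test based on CTA analysis population." No covariate is named in either place.

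The index value is always present when a change is analysed. Protocol 4.1.4: "For follow-up CTA at the end of the study, subjects would need to have undergone index CTA." Protocol Table 9, footnote q: "Follow-up coronary CTA imaging will be done only for subjects with index CTA." SAP 3.4.2.2: "Missing data will not be imputed."

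On timing, Protocol Table 9, footnote p, says that the index scan "may be done up to 5 days post Dose 1) but no earlier than 40 hours post Dose 1", with 48-72 hours preferred. Protocol 3.1.1 sets the second dose thus: "On Day 3 (48±8 hours post" the first. Protocol 4.8.1 defines baseline: "Baseline values will be defined as the last valid assessment prior to the first administration of investigational product on Day 1." SAP 3.1 uses the same definition with an added clause for missing data.

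Allocation within Cohort B was 2:1 (Protocol 4.6.1) and became 1:1 under Protocol 4.2.1.1.

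**The concern.** A t-test on follow-up minus index is a regression in which the coefficient of the index value is set to 1 instead of estimated. If the true slope of follow-up on index is not 1, the comparison carries avoidable variance, and a chance imbalance in index NCPV passes in part into the estimated difference.

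The data for this endpoint are limited. Only Cohort B subjects who meet the CTA criteria and have both scans contribute, and Protocol 4.2.1.1 reports a greater dropout rate in that cohort. What is at stake is the width of the interval on one secondary endpoint.

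**Working it through.** **No plan figure to reproduce.** The NCPV difference, SD, power and drop-out in Protocol 4.8.2 are redacted, and SAP 2.4 has no readable content. Everything below rests on assumed inputs: the index/follow-up correlation r; the ratio k of follow-up SD to index SD; a starting power of 80% at one-sided 0.05 (the alpha is from SAP 3.1, the 80% is assumed); and, for unequal slopes, the slopes, residual SD and arm sizes.

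**1. Common slope.** Let the index SD be s.
- Var(change) = s²(1 + k² - 2rk)
- Var(ANCOVA residual) = s²k²(1 - r²)
- With k = 1 the ratio is (1 - r²)/(2(1 - r)) = (1 + r)/2, a reduction of (1 - r)/2.
- Power after adjustment = Φ(2.4865/√ratio - 1.645), where 2.4865 = 1.645 + 0.8416 to rounding.

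| r (k = 1) | variance ratio | reduction | 80% power becomes |
|---|---|---|---|
| 0.95 | 0.975 | 2.5% | 80.9% |
| 0.9 | 0.950 | 5% | 81.8% |
| 0.8 | 0.900 | 10% | 83.6% |
| 0.7 | 0.850 | 15% | 85.4% |
| 0.5 | 0.750 | 25% | 89.0% |

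For k between 0.9 and 1.1 and r between 0.5 and 0.95, the reduction runs from 0.04% (k = 1.1, r = 0.9, slope rk = 0.99; power 80.0%) to 33% (k = 0.9, r = 0.5; power 91.9%). With slope 1 in both arms the large-sample ratio is 1.00 and the simulated ratio 1.005 to 1.010, a cost of about 1%.

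**2. Validity.** Simulation at 90 vs 45 subjects gave Type I error of 4.6% to 5.4% across both methods.

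**3. Chance imbalance.** With k = 1 the slope is r, so an index imbalance of 0.25 SD moves the change-score difference by (1 - r) × 0.25: 0.125 SD at r = 0.5 and 0.025 SD at r = 0.9. ANCOVA removes this.

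**4. Unequal slopes at 2:1.** Take index SD 1, slopes 0.6 (active) and 1.1 (placebo), residual SD 0.6, 120 vs 60.
- Change score: (0.16 + 0.36)/120 + (0.01 + 0.36)/60 = 0.01050.
- Common-slope ANCOVA: pooled slope (120 × 0.6 + 60 × 1.1)/180 = 0.767. Variance (0.0278 + 0.36)/120 + (0.1111 + 0.36)/60 = 0.01108, ratio 1.056.
- With a treatment-by-index term centred at the overall mean: 0.36 × (1/120 + 1/60) + 0.5²/180 = 0.00900 + 0.00139 = 0.01039, ratio 0.989.

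So common-slope ANCOVA can be less precise than the t-test under 2:1 allocation, and the interaction term removes that loss. With the slopes reversed (1.1 active, 0.6 placebo) the large-sample ratios are 0.943 and 0.884.

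**5. Standard error of the interaction model.** The usual model standard error omits the 0.5²/180 term, which comes from centring at an observed mean. The omitted share of the variance is 0.00139/0.01039 = 13% at residual SD 0.6. At 0.4 it is 0.00139/(0.00400 + 0.00139) = 26%. Simulation gave shortfalls of similar size. At equal slopes the share is zero.

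**6. Timing of the index scan.** The allowed window is 40 to 120 hours after Dose 1, and the Day 3 dose is due at 40 to 56 hours. After hour 56 an on-time Day 3 dose has always been given, which covers 120 - 56 = 64 of the 80 allowed hours and 72 - 56 = 16 of the 24 preferred hours. If treatment has already shifted index NCPV by d, the change score subtracts d and a common-slope ANCOVA subtracts slope × d, so the adjusted estimate minus the change-score estimate is (1 - slope) × d. For an assumed d of -0.2 SD this is -0.01 SD at slope 0.95, -0.04 at 0.8 and -0.10 at 0.5.

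**The case against.** The strongest reply is that this is a preference. The endpoint is defined as a change, a t-test on change estimates that directly, and nothing readable in the power statement suggests that adjustment was planned. The benefit cannot be located within its range, because the inputs are redacted. All of that stands, and it is why the point is optional.

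The second objection is that the covariate is measured after treatment has begun, so an imbalance in it may itself be a drug effect. SAP 3.4.1.5 and 3.4.2.4 rule out between-arm comparisons in subgroups defined after randomization, and an interaction with a post-dose value sits uneasily with that principle. This stands as a limit to be stated. It does not defeat the suggestion: the planned change score subtracts the same scan with its coefficient fixed at 1, and the adjusted model would report one average effect, not effects by subgroup.

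The third is that an interaction model with its default standard error could give intervals that are too narrow. That is correct when slopes differ, so the standard error has to be named in the SAP text itself.

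A supportive adjusted analysis in SAP 3.4.3 cannot be excluded, since that section has no readable content. The analysis specified in 3.4.2.3 is unadjusted either way.

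A reader might infer that the planned test is biased or inflates Type I error. The documents do not support that: the comparison is a valid two-sample test. Nor do they support saying that a known amount of power is being lost.

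**Conclusion.** The plan specifies an unadjusted comparison of change in NCPV although the index value exists for every analysed subject. Adjustment is a low-cost, optional improvement in precision on a secondary endpoint. With equal SDs and a common slope the variance falls by 2.5% to 25% for r from 0.95 to 0.5. The gain is close to nil when the slope is near 1, with a cost of about 1% at slope 1 exactly. No figure here is an estimate for this trial; all depend on assumed correlations, SD ratios, slopes and arm sizes.

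A reader might also infer that adjustment repairs the selection created by requiring a full treatment course for the CTA Analysis Population (SAP 3.2). It does not; it removes only the part of an imbalance that runs through index NCPV.

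**What to change.** In SAP 3.4.2.3, with matching text in Protocol 4.8.3.3:

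- Analyse change in NCPV (mm³) by ANCOVA on treatment and index NCPV, keeping the difference in mm³ as the effect measure.
- Because allocation was 2:1 and later 1:1, include a treatment-by-index term centred at the overall index mean.
- Specify in the same paragraph a bootstrap or delta-method standard error that includes the variance from centring.
- Keep the unadjusted t-test on change as a stated sensitivity analysis.
- State that the index CTA is taken 40 hours to 5 days after Dose 1, may also follow the Day 3 dose, and is not a baseline under Protocol 4.8.1 or SAP 3.1. Add that, under a common slope, the two estimates differ by (1 - slope) times any early treatment shift in index NCPV.

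Minor note: exempt NCPV change from the log-normal branch, since zero or negative changes cannot be log-transformed, and name the rank-based fallback, for example a Wilcoxon rank-sum test on the change.

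The cost is one SAP paragraph, one protocol sentence and slightly more programming. No new data are needed.
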